4.7.1.2 Withdrawal from Study

Every effort should be made to obtain information on study subjects who withdraw from the study. The primary reason for withdrawal from the study should be documented on the appropriate eCRF.

Study subjects will not be followed for any reason after consent has been withdrawn.

When a patient voluntarily withdraws from the study, or is withdrawn by the Investigator, samples collected until the date of withdrawal will be analyzed, unless patient specifically requests for these to be discarded or local laws require their immediate destruction. A patient's withdrawal from Study BP39405 does not, by itself, constitute withdrawal of specimens donated to the RBR.

Study subjects who withdraw from the study for safety reasons will not be replaced. Study subjects who withdraw from the study for other reasons may be replaced.

4.7.2 Study and Site Discontinuation

The Sponsor has the right to terminate this study at any time. Reasons for terminating the study may include, but are not limited to, the following:

- The incidence or severity of adverse events in this or other studies indicates a potential health hazard to study subjects.
- Clinically significant changes in safety parameters considered to be related to RO7062931 and not considered acceptable by the Investigator and/or Sponsor.

Study subject enrollment is unsatisfactory.

The Sponsor will notify the Investigator and Health Authorities if the study is placed on hold, or if the Sponsor decides to discontinue the study or development program.

The Sponsor has the right to replace a site at any time. Reasons for replacing a site may include, but are not limited to, the following:

- Excessively slow recruitment
- Poor protocol adherence
- Inaccurate or incomplete data recording
- Non-compliance with the International Conference on Harmonisation (ICH) guideline for Good Clinical Practice

5. ASSESSMENT OF SAFETY

5.1 SAFETY PARAMETERS AND DEFINITIONS

Safety assessments will consist of monitoring and recording adverse events, including serious adverse events (SAEs) and non-serious adverse events of special interest; measurement of protocol-specified safety laboratory assessments; measurement of protocol-specified vital signs, ECGs; and other protocol-specified tests that are deemed critical to the safety evaluation of the study.

Certain types of events require immediate reporting to the Sponsor, as outlined in Section [5.4](#).

5.1.1 Adverse Events

According to the ICH guideline for Good Clinical Practice, an adverse event is any untoward medical occurrence in a clinical investigation subject administered a pharmaceutical product, regardless of causal attribution. An adverse event can therefore be any of the following:

- Any unfavorable and unintended sign (including an abnormal laboratory finding), symptom, or disease temporally associated with the use of a medicinal product, whether or not considered related to the medicinal product.
- Any new disease or exacerbation of an existing disease (a worsening in the character, frequency, or severity of a known condition), except as described in Section [5.3.5.9](#).
- Recurrence of an intermittent medical condition (e.g., headache) not present at baseline.
- Any deterioration in a laboratory value or other clinical test (e.g., ECG, X-ray) that is associated with symptoms or leads to a change in study treatment or concomitant treatment or discontinuation from study drug.
- Adverse events that are related to a protocol-mandated intervention, including those that occur prior to assignment of study treatment (e.g., screening invasive procedures such as biopsies).

5.1.2 Serious Adverse Events (Immediately Reportable to the Sponsor)

A serious adverse event is any adverse event that meets any of the following criteria:

- Fatal (i.e., the adverse event actually causes or leads to death).
- Life-threatening (i.e., the adverse event, in the view of the Investigator, places the patient at immediate risk of death).

This does not include any adverse event that had it occurred in a more severe form or was allowed to continue might have caused death.

- Requires or prolongs inpatient hospitalization (see Section [5.3.5.10](#)).
- Results in persistent or significant disability/incapacity (i.e., the adverse event results in substantial disruption of the study subject's ability to conduct normal life functions).
- Congenital anomaly/birth defect in a neonate/infant born to a mother exposed to study drug.
- Significant medical event in the Investigator's judgment (e.g., may jeopardize the study subject or may require medical/surgical intervention to prevent one of the outcomes listed above).

The terms "severe" and "serious" are not synonymous. Severity refers to the intensity of an adverse event (rated as mild, moderate, or severe, or according to a pre-defined grading criteria (see [Table 2](#)); the event itself may be of relatively minor medical significance (such as severe headache without any further findings). Severity and seriousness need to be independently assessed for each adverse event recorded on the eCRF.

Serious adverse events are required to be reported by the Investigator to the Sponsor immediately (i.e., no more than 24 hours after learning of the event; see Section [5.4.2](#) for reporting instructions).

5.1.3 Non-Serious Adverse Events of Special Interest (Immediately Reportable to the Sponsor)

Non-serious adverse events of special interest are required to be reported by the Investigator to the Sponsor immediately (i.e., no more than 24 hours after learning of the event; see Section 5.4.2 for reporting instructions). Adverse events of special interest for this study include the following:

- *Cases of an isolated elevated ALT or AST ≥ 10 ULN (Section 5.2 and 5.3.5.6).*
- *Cases of an elevated ALT or AST in combination with either an elevated bilirubin or clinical jaundice, as defined in Section 5.3.5.6.*
- *Suspected transmission of an infectious agent by the study drug, as defined below:
Any organism, virus, or infectious particle (e.g., prion protein transmitting transmissible spongiform encephalopathy), pathogenic or non-pathogenic, is considered an infectious agent. A transmission of an infectious agent may be suspected from clinical symptoms or laboratory findings that indicate an infection in a patient exposed to a medicinal product. This term applies only when a contamination of the study drug is suspected.*
- *Severe injection site reactions*
- *Grade 3 renal adverse events defined as creatinine $\geq 50\%$ from baseline *and/or* eGFR < 60 mL/min/1.73 m².*

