5.2.1.2 Alanine Transaminase (ALT) Elevations

Abrupt elevation of serum ALT above normal is known to occur spontaneously in patients with CHB during the course of disease, and/or during anti-viral therapy. Transient ALT elevations are not always harmful and may be due to:

- *The underlying disease*
- *Immune clearance of infected hepatocytes*
- *Drug-induced immune-mediated hepatitis*
- *DILI*

Isolated ALT elevations of 2-3 times the baseline value that are self-limited may reflect a desirable treatment-related immunologic response rather than drug toxicity. However, progressive increases or ALT elevations associated with increases in bilirubin without alkaline phosphatase increase should primarily be considered adverse events, i.e. potential DILI.

In the event of ALT elevation > 5x ULN, more frequent monitoring of liver tests should be performed based on medical judgment and other causes of ALT elevations should be investigated. For patients with ALT > 5 × ULN, the following management plan is recommended:

ALT elevations during treatment

- *Isolated ALT elevation with preserved hepatic function (e.g. no significant changes in bilirubin, INR/PT, albumin, and ALP):*
 - *Closely monitor liver function tests (LFTs) (i.e. ALT/AST, bilirubin, albumin, ALP and INR/PT):*
 - *ALT 5 to 10 x ULN: Repeat LFTs every week.*
 - *ALT >10 x ULN: Temporarily interrupt RO7062931 or RO7062931 and PEG-IFN treatment and repeat LFTs twice weekly until ALT level < 5 x ULN. Continue NUC treatment. Consider re-introducing RO7062931 or RO7062931 and PEG-IFN therapy following discussion with medical monitor based on subsequent laboratory results.*
- *ALT flare accompanied by declining liver synthetic and excretory functions (increased bilirubin >2 x ULN, or albumin decline >0.5 g/dL, or INR >1.5) or other signs of hepatic impairment (severe fatigue, nausea, vomiting, right upper quadrant pain):*
 - *RO7062931 or RO7062931 and PEG-IFN will be permanently discontinued, continue NUC treatment.*
 - *Closely monitor liver function tests:*
 - *ALT 5 to 10 x ULN: Repeat LFTs every week.*
 - *ALT >10 x ULN: Repeat LFTs twice weekly until ALT level < 5 x ULN.*
 - *Investigate the participant for potential etiologies of the laboratory changes.*
 - *If alternative reasons/diagnoses cannot explain the laboratory changes, a potential DILI will be considered.*

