- Treatment-emergent ALT $> 3 \times$ Baseline and $> 3x$ ULN value in combination with total bilirubin $> 2 \times$ ULN.
- Treatment-emergent ALT $> 3 \times$ Baseline and $> 3x$ ULN value in combination with clinical jaundice.

**For Part 2c (treatment-naïve and immune-active CHB patients), the threshold of ALT $> 3 \times$ ULN baseline will be capped at $10 \times$ ULN.*

The most appropriate diagnosis or (if a diagnosis cannot be established) the abnormal laboratory values should be recorded on the Adverse Event eCRF (see Section 5.3.5.1) and reported to the Sponsor immediately (i.e., no more than 24 hours after learning of the event), either as a serious adverse event or a non-serious adverse event of special interest (see Section 5.4.2).

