5.3.5.9 Lack of Efficacy or Worsening of Chronic Hepatitis B Infection

As this is the first study of RO7062931 in humans as well as in CHB patients and these patients are virologically suppressed, the effect on HBsAg is being explored as part of the secondary endpoints in this study. The short duration of treatment RO7062931 is not anticipated to provide the patients with therapeutic benefit, but rather to give evidence on the effect of multiple doses of RO7062931 on HBsAg.

Therefore, lack of RO7062931 efficacy in terms of changes in HBsAg does not qualify for adverse event in Part 2 of this study.

Medical occurrences or symptoms of deterioration in a course of chronic HBV infection should be recorded as adverse events if judged by the Investigator to have unexpectedly worsened in severity or frequency or changed in nature at any time during the study.

Virological breakthrough (Section 4.6.1.5.3), and abnormal liver function tests (as defined in Section 5.3.5.6) should be reported as adverse events. Hepatic flares should be reported as adverse events of special interest (Section 5.1.3).

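### The sections on liver events disagree on what is an AESI: with ALT >5 to <10 x ULN, a flare stopped for INR >1.5 or an albumin fall meets no listed 24-hour trigger

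*Combined protocol and SAP*

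**What the plan says.** Section 5.1.3 requires AESIs to reach the Sponsor within 24 hours. Its two liver entries are "Cases of an isolated elevated ALT or AST ≥ 10 ULN", with a cross-reference to Sections 5.2 and 5.3.5.6, and "Cases of an elevated ALT or AST in combination with either an elevated bilirubin or clinical jaundice, as defined in Section 5.3.5.6". For Part 2, 5.3.5.6 defines the combination as ALT above 3 x baseline and above 3 x ULN, with either total bilirubin >2 x ULN or clinical jaundice.

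The sections that decide when treatment stops use a wider set of markers:

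- **5.2.1.2**, in a plan that applies from ALT >5 x ULN and is introduced as recommended, separates two situations. One is "Isolated ALT elevation with preserved hepatic function (e.g. no significant changes in bilirubin, INR/PT, albumin, and ALP". The other is "ALT flare accompanied by declining liver synthetic and excretory functions (increased bilirubin >2 x ULN, or albumin decline >0.5 g/dL, or INR >1.5"; clinical symptoms pointing to impaired liver function also qualify. For the second it says "RO7062931 or RO7062931 and PEG-IFN will be permanently discontinued, continue NUC treatment".
- **4.7.1.1**, the mandatory list for Part 2, includes Grade 3 ALT (>5 to <10 x ULN) with INR >1.5. It has no albumin limb.
- **5.2.1.1** makes potential DILI a compulsory SAE report. Its Part 2 definition needs total bilirubin >2 x ULN.
- **5.3.5.9** says "Hepatic flares should be reported as adverse events of special interest" and cites 5.1.3. No hepatic flare entry appears in 5.1.3, and no current section gives the term a threshold for reporting.

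**The concern.** The stopping sections treat loss of synthetic function (INR, albumin) as a reason to end treatment. The AESI list looks only at transaminases, bilirubin and jaundice. A patient can therefore be taken off RO7062931 for a liver event without meeting any listed liver trigger for 24-hour notice.

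Two things are at stake. The first is timing. Part 2c is open-label and uncontrolled, adds PEG-IFN in Cohort 10 for up to 48 weeks, and bases expansion on accumulated safety data (3.1.1.3, 3.1.2). The milestone safety teleconferences in 3.1.4 name the Part 1 cohorts, Part 2a and Part 2b, but not Part 2c. The second is counting. Section 3.3.1 makes the incidence of adverse events, including AESIs, a safety outcome, and safety is the primary objective. If sites differ on whether a flare is an AESI, that count has no fixed meaning.

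**Working it through.** No arithmetic of power or precision applies, so the check traces each rule for a set of patients.

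**Inputs**
- AESI bullet 1 (5.1.3): isolated ALT or AST >=10 x ULN.
- AESI bullet 2 (5.1.3 with 5.3.5.6): ALT >3 x baseline and >3 x ULN, with total bilirubin >2 x ULN or jaundice.
- DILI laboratory criterion (5.2.1.1): ALT >3 x the higher of baseline and ULN, with total bilirubin >2 x ULN.
- Declining function (5.2.1.2), from ALT >5 x ULN: bilirubin >2 x ULN, or albumin decline >0.5 g/dL, or INR >1.5, or clinical signs.
- Mandatory stop, INR limb (4.7.1.1): ALT >5 to <10 x ULN and INR >1.5.

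**Assumptions**: baseline ALT 1 x ULN and no jaundice. Bullet 1 is read in two ways. In the *narrow* reading, 'isolated' means preserved function, as in 5.2.1.2. In the *wide* reading, it means only without raised bilirubin or jaundice.

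| ALT (x ULN) | Only other change | 5.2.1.2 discontinues | 4.7.1.1 INR limb | AESI, narrow | AESI, wide | DILI laboratory criterion |
|---|---|---|---|---|---|---|
| 6 or 9.9 | INR 1.6 | yes | yes | no | no | no |
| 6 or 9.9 | albumin down 0.6 g/dL | yes | no | no | no | no |
| 6 or 9.9 | bilirubin 2.1 x ULN | yes | no | yes | yes | yes |
| 10 or 12 | none | no | no | yes | yes | no |
| 10 or 12 | INR 1.6 | yes | no | no | yes | no |
| 10 or 12 | albumin down 0.6 g/dL | yes | no | no | yes | no |
| 10 or 12 | bilirubin 2.1 x ULN | yes | no | yes | yes | yes |

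**One patient in full**: ALT 7 x ULN, INR 1.6, bilirubin 1.4 x ULN, no jaundice. Bullet 1 fails because 7 < 10. Bullet 2 and the DILI criterion fail because 1.4 is not >2. The INR limb of 4.7.1.1 is met because 5 < 7 < 10 and 1.6 > 1.5. The stop is mandatory, yet nothing on the AESI list or in the DILI definition applies, under either reading of 'isolated'.

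**At ALT 12 x ULN** with the same INR and bilirubin, the answer depends on the reading. For the narrow one, bullet 1 cross-refers to 5.2, and 5.2.1.2 pairs the word with preserved function, while current 5.3.5.6 contains no isolated-ALT criterion. For the wide one, 'isolated' in 5.1.3 stands next to a bullet about bilirubin and jaundice. In addition, if the word already implied preserved function, 5.2.1.2 would not need to say so.

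**5.3.5.9 against 5.1.3**: the first sends flares to the second, and the second has no flare entry. An investigator who follows 5.3.5.9 reports the event; one who works from the list in 5.1.3 does not.

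**The case against.** The strongest reply is that the event need not go unreported. Section 5.3.5.9 itself calls hepatic flares AESIs, 5.2.1.2 describes the event as an "ALT flare accompanied by declining liver synthetic and excretory functions", and the list in 5.1.3 is not stated to be exhaustive. An investigator may also call the event serious as medically significant (5.1.2), consider potential DILI if it is unexplained (5.2.1.2), or contact the Sponsor at once about a safety concern (3.1.4). The Sponsor should be told of discontinuations from study drug (4.7.1.1), and central laboratory data go to it directly (7.1). A laboratory change that alters treatment must be recorded as an adverse event (5.3.5.4), so the case stays in the safety dataset.

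Most of this stands, and it rules out several stronger conclusions that a reader might draw:

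- *That these flares produce no 24-hour report, or reach the Sponsor only through the eCRF.* The routes above contradict both. What they lack is a guarantee: the SAE, DILI and safety-concern routes are discretionary, the discontinuation and laboratory-transfer provisions set no 24-hour limit, and 5.3.5.9 relies on an undefined term and a missing entry.
- *That at ALT >=10 x ULN the list certainly drops the sicker patient.* This holds only on the narrow reading.
- *That every declining-function trigger other than bilirubin falls outside the AESI list at any ALT.* A symptoms-only flare at ALT >=10 x ULN may still count as isolated, because the examples of preserved function in 5.2.1.2 are all laboratory values.
- *That an albumin fall makes discontinuation mandatory.* The 5.2.1.2 plan is headed as recommended, and 4.7.1.1 has only the INR limb.

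**Conclusion.** The inconsistency is real and limited in extent. For ALT >5 to <10 x ULN with INR >1.5 or an albumin decline >0.5 g/dL, bilirubin not >2 x ULN and no jaundice, no listed AESI or defined DILI criterion guarantees a 24-hour report or a place in the AESI count. For INR this sits beside a mandatory stop; for albumin, beside a recommended permanent discontinuation. At ALT >=10 x ULN the same gap is conditional on how 'isolated' is read. Separately, the reference in 5.3.5.9 to a hepatic flare AESI leads to nothing in 5.1.3, whichever reading is taken.

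The certain part does not depend on the assumed baseline: bullet 1 fails on ALT level, and bullet 2 and DILI fail on bilirubin. The documents give no expected frequency for such flares, so the number of affected reports cannot be stated. All-AE and laboratory summaries would still show these cases. The weakness lies in prompt notice and in a consistent AESI count.

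**What to change.** Reconcile 5.1.3, 5.2.1.2, 4.7.1.1 and 5.3.5.9, for reporting only:

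1. In 5.1.3, remove 'isolated', or define it, so that ALT or AST >=10 x ULN is an AESI whatever the liver function.
2. Add one AESI bullet that refers to the declining-function criteria already in 5.2.1.2 and the corresponding Grade 3 ALT criteria in 4.7.1.1, without restating or altering them.
3. Point the hepatic flare sentence in 5.3.5.9 to these bullets, so that the term has a reporting definition.

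No treatment rule, stopping rule or laboratory threshold changes. The cost is protocol wording, guidance on the AESI form, and a few more 24-hour reports drawn from data already collected.

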5.2 SAFETY PLAN

Measures will be taken to ensure the safety of the healthy volunteers/patients participating in this trial; in particular, the use of appropriate inclusion and exclusion criteria and close monitoring of the study subjects. HVs/ patients will be monitored by AE monitoring, vital sign monitoring, ECG monitoring, and hematology and clinical chemistry parameters.

The Investigator has the right to withdraw a HV/ patient for safety reasons at any time. Also, the Investigator and Sponsor may terminate a particular cohort or the study as whole at any time if considered warranted for safety reasons. For example, a particular cohort may be terminated in case of safety related drop-outs if the safety events were similar in nature.

5.2.1 Management of Specific Adverse Events

5.2.1.1 *Potential Drug-Induced Liver Injury (DILI)*

Wherever possible, timely confirmation (within 48 to 72 hours) of initial liver-related laboratory abnormalities should occur prior to the reporting of a potential DILI event. All occurrences of potential DILIs, meeting the defined criteria, must be reported as SAEs, and discontinuation of all study medications (RO7062931, NUC, or PEG-IFN, where applicable) must be considered.

In this study, potential DILI is defined as follows:

- *For healthy volunteers (Part 1): ALT > 3 × ULN accompanied total bilirubin > 2 × ULN*
- *For CHB patients (Part 2): ALT > 3 × baseline / ULN (whichever is higher) accompanied by total bilirubin > 2 × ULN*

AND

- *No other immediately apparent possible causes of ALT elevation and hyperbilirubinemia, including, but not limited to acute viral hepatitis, cholestasis, pre-existing hepatic disease excluding HCV/HEV or the administration of other drug(s), herbal medications, or substances known to be hepatotoxic.*

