The reliability of sexual abstinence should be evaluated in relation to the duration of the clinical trial and the preferred and usual lifestyle of the patient. Periodic abstinence (e.g., calendar, ovulation, symptothermal, or post-ovulation methods) and withdrawal are not acceptable methods of contraception.

4.2.2.3 *Part 2c - CHB patients only:*

1. *Ability and willingness of patients to provide written informed consent.*
2. *Adult male and female patients, 18 to 65 years of age, inclusive.*
3. *A BMI between 18 to 32 kg/m² inclusive.*
4. *CHB infection (HBsAg-positive for \geq 6 months).*
5. *For cohorts only enrolling NUC-suppressed CHB patients, patients must meet the following criteria:*
 - a. *Patients treated with a single NUC (entecavir, tenofovir alafenamide, or tenofovir disoproxil fumarate) for \geq 12 months. Patients must be on the same NUC therapy for at least 3 months before screening.*
 - b. *HBV DNA $<$ LLOQ at screening and in preceding 6 months (at least one measurement $>$ 30 days prior to screening).*
 - c. *ALT \leq 2 x ULN for $>$ 6 months prior to screening and confirmed at screening. Total bilirubin within normal range at screening, except for patients with Gilbert's syndrome (TB \leq 47 μ mol/L [2.75 mg/dL]).*
6. *For cohorts only enrolling treatment-naïve and immune-active patients (e.g., Cohort 11), patients must meet the following criteria:*
 - a. *HBV DNA at screening \geq 2 x 10⁴ IU/mL for HBeAg positive patients, or \geq 2 x 10³ IU/mL for HBeAg negative patients.*

- b. *Elevated serum ALT >2 ULN to \leq 5 ULN, 2 values within 6 months, at least one of which is at screening and both results must be at least 14 days apart. Total bilirubin within normal range at screening, except for patients with Gilbert's syndrome (TB \leq 47 μ mol/L [2.75 mg/dL]).*
7. *Screening laboratory values (hematology, chemistry, urinalysis) obtained up to 28 days prior to first study treatment within normal ranges, with the exception of otherwise specified criteria or judged to be not clinically significant by PI and Medical Monitor.*
 8. *Liver biopsy, Fibroscan[®] or equivalent test obtained within the past 6 months demonstrating liver disease consistent with chronic HBV infection without evidence of bridging fibrosis or cirrhosis (\geq Metavir 3, recommended cut-off for fibroscan 8.5 kPa).*

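### For treatment-naïve, immune-active Part 2c patients with baseline ALT above 3.33 × ULN, the potential-DILI threshold (5.2.1.1) lacks the 10 × ULN cap used in 5.3.5.6, so some events escape the mandatory-SAE definition

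*Combined protocol and SAP*

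**What the plan says.** Section 5.2.1.1 defines potential DILI for all CHB patients in Part 2. ALT must exceed 3 times baseline or ULN, "whichever is higher) accompanied by total bilirubin" above 2 × ULN, and there must be no other immediately apparent cause. The consequence is fixed: "All occurrences of potential DILIs, meeting the defined criteria, must be reported as SAEs". Stopping all study medication, including the NUC, must also be considered. No cap is stated.

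Section 5.3.5.6 sets a parallel Part 2 rule: ALT above 3 × baseline and above 3 × ULN, with bilirubin above 2 × ULN or clinical jaundice. It then adds a limit: "For Part 2c (treatment-naïve and immune-active CHB patients), the threshold of ALT" is capped at 10 × ULN. Events under this rule go to the sponsor within 24 hours, "either as a serious adverse event or a non-serious adverse event of special interest".

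Inclusion criterion 6b in Section 4.2.2.3 admits treatment-naïve, immune-active patients with ALT above 2 and up to 5 × ULN, on "2 values within 6 months, at least one of which is at screening". Under Section 3.1.1.3 only optional Cohorts 11 and 12 may enrol them.

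Section 5.2.1.2 says that ALT rises "associated with increases in bilirubin without alkaline phosphatase increase should primarily be considered adverse events, i.e. potential DILI". Its recommended plan for a flare with bilirubin above 2 × ULN is "RO7062931 or RO7062931 and PEG-IFN will be permanently discontinued, continue NUC treatment".

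**The concern.** Two rules for the same laboratory picture use different ALT thresholds in the same patients. In a patient with a high baseline, ALT can pass the 10 × ULN cap in 5.3.5.6 and still be below 3 × baseline. With bilirubin above 2 × ULN and no apparent cause, that event is reportable under 5.3.5.6 but does not meet the 5.2.1.1 definition. SAE status then depends on the SAE-or-AESI choice in 5.3.5.6, or on the Section 5.1.2 criterion for an event that "may jeopardize the study subject or may require medical/surgical intervention".

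Two things follow from the label. Section 5.7 bases expedited reporting partly on the investigator's assessment of seriousness. Section 4.7.1.1 makes stopping study drug mandatory for an SAE considered related to RO7062931. The ALT-specific stopping rules in 4.7.1.1 do not fill the space: the Grade 4 rule excludes Part 2c, and the Grade 3 rule ends below 10 × ULN. What is left for this picture is the 5.2.1.2 plan, which is introduced as a recommendation.

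**Working it through.** The plan states no figure for this gap, so there is none to reproduce. The check is threshold arithmetic in multiples of ULN, with B for baseline ALT.

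**Inputs**
- 5.2.1.1: ALT limb at 3 times the higher of baseline and ULN, no cap.
- 5.3.5.6: ALT above 3 × baseline and above 3 × ULN, capped at 10 × ULN for this population.
- 4.2.2.3, criterion 6b: B above 2 and up to 5, assuming baseline equals the qualifying screening value.
- 4.2.2.3, criterion 5c: ALT at most 2 × ULN in NUC-suppressed patients.

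**Reading of the cap.** The sentence in 5.3.5.6 attaches the multiple of 3 to ULN and baseline run together. A cap at 10 × ULN could never bind on 3 × ULN, so I read it as a cap on 3 × baseline. That reading is inferred.

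**Formulas**
- 5.2.1.1 threshold = 3 × max(B, 1)
- 5.3.5.6 threshold = min(3 × max(B, 1), 10)
- The two part when 3B > 10, that is B > 10/3 = 3.33.

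| B (× ULN) | 5.2.1.1 | 5.3.5.6 | Gap | Fold-rise at the cap (10/B) |
|---|---|---|---|---|
| 3 | 9 | 9 | 0 | cap not reached |
| 3.33 | 10 | 10 | 0 | 3.0 |
| 3.5 | 10.5 | 10 | 0.5 | 2.86 |
| 4 | 12 | 10 | 2 | 2.5 |
| 4.5 | 13.5 | 10 | 3.5 | 2.22 |
| 5 | 15 | 10 | 5 | 2.0 |

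At the eligibility ceiling the uncapped threshold is 5/10 = 50% above the cap.

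**Example.** With B = 5, ALT of 14 × ULN is 14/5 = 2.8 × baseline. It is above the cap but not above 3 × baseline. With bilirubin above 2 × ULN it meets 5.3.5.6 and fails 5.2.1.1.

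**Scope.** Baselines above 3.33 make up (5 − 3.33)/(5 − 2) = 56% of the eligible ALT interval. Patients in Cohorts 9 and 10 enter with ALT at most 2 × ULN, so their threshold is at most 3 × 2 = 6 × ULN and the cap is never reached. Cohorts 11 and 12 start with about 2 × 8 = 16 patients.

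**After the fix.** Both thresholds become min(3B, 10), and the gap is zero at every eligible baseline.

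**The case against.** The strongest reply is that the two rules do different jobs. Section 5.3.5.6 is a reporting net with a jaundice arm and an explicit SAE-or-AESI choice; 5.2.1.1 is a narrower definition with a fixed consequence. A stricter SAE tier inside a wider reporting tier would be coherent. That stands as a possibility, but no passage states it, and the 5.2.1.2 wording on raised bilirubin without an ALP increase points the other way.

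Second, SAE status under 5.2.1.1 is never purely rule-based, because the limb on other apparent causes needs investigator judgement. In untreated, immune-active CHB the underlying disease is itself a listed cause of ALT rises. This stands. A reader might infer that the missing cap replaces a rule with judgement; the documents support only that it removes the ALT limb as a trigger in the band.

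Third, the band is already covered in most respects. Sections 5.1.3, 5.3.5.6 and 5.4 give 24-hour reporting for SAEs and AESIs alike. Under 5.7 the sponsor evaluates both and may upgrade. Section 5.2.1.2 directs a permanent stop of RO7062931 and PEG-IFN, and asks that potential DILI be considered if no alternative explains the changes. This stands too. It rules out the tempting inference that such events would go undetected or be reported late, or that the plan gives no stopping instruction for them.

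Fourth, the cap sentence is garbled and has a footnote-style asterisk with no visible anchor. It could be read as a general remark on the ALT threshold in these patients. That is a reason to repair the sentence, since nothing in 5.2.1.1 refers to it.

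**Conclusion.** The mismatch is real and minor. For treatment-naïve, immune-active Part 2c patients with baseline ALT above 3.33 × ULN, the ALT limb of the potential-DILI definition sits above the capped reporting rule, by up to 5 × ULN at baseline 5 × ULN. The consequence is limited to SAE-versus-AESI classification, seriousness-based expedited reporting, and the binding stop for a related SAE.

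This rests on reading the cap as applying to 3 × baseline and on baseline ALT equalling an eligible screening value. It also requires that Cohorts 11 or 12 open to this population; 16 patients assumes that both do so exclusively. The 56% is a share of the ALT interval. A reader might take it as a share of patients or as an event rate, but the protocol gives no baseline ALT distribution. An affected event also needs ALT inside the band, bilirubin above 2 × ULN and no apparent other cause.

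**What to change.** Add to the Part 2 bullet of 5.2.1.1 that, for treatment-naïve, immune-active Part 2c patients, the 3 × baseline ALT threshold is capped at 10 × ULN. In the cap sentence of 5.3.5.6, delete ULN after the multiple of 3 so that it reads 3 × baseline. If a narrower SAE rule is intended, state that in 5.2.1.1 instead.

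The change is two lines of text, applies a cap the sponsor already chose, and adds no scheduled tests. It has two costs. A few more events may become SAEs: at baseline 5 × ULN, any rise beyond a doubling of ALT would satisfy the ALT limb, given raised bilirubin and no apparent cause. The 5.2.1.1 requirement to consider stopping all study medication, NUC included, would also reach these patients, whereas 5.2.1.2 says to continue the NUC. One sentence saying which instruction governs the NUC would settle that.
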